5.2.3 Sensitivity Analysis

Pattern Mixture Analysis

A sensitivity analysis will be performed using a pattern mixture model with multiple imputation for missing data under the missing not at random (MNAR) assumption using the same approach as described for the primary analysis in Section 5.2.1. See Appendix 12.3 for further details.

Modified Multiple Imputation Analysis

The second sensitivity analysis may be carried out imputing C3G Histological Index of Disease Activity data for subjects who had clinical significant increase or new introduction of treatments

for C3G including MMF and/or prednisone after screening biopsy and prior to week 26 renal biopsy; should any of these changes invalidate histological activity scores at week 26. Identification of these medications will be performed and impacted subjects will be identified prior to Week 26 Primary Endpoint data freeze. Similar methodology as described for the primary analysis (ANCOVA) will be carried out. The same multiple imputation as specified for the primary analysis (Section 5.2.1) may be performed imputing C3G Histological Index of Disease Activity component scores and Disease Chronicity component scores after the initiation of the restricted medication. The imputed values will be used to calculate the C3G Histological Index of these variables. Identification of these medications will be performed and impacted subjects will be discussed and finalized prior to database lock.

Modified Multiple Imputation method may be explored for the percent change and change from Week 26 to Week 52 during the avacopan treatment period.

Additional Modified Multiple Imputation Analysis may be conducted to explore other aspects of changes of treatments for C3G, such as clinical significant dose decreases of immunosuppressants, glucocorticoids, or ACE inhibitors/ARBs in Period A.

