5.3.1.1 Primary Analysis

The primary analysis will be based on the ITT population in the elevated C5b-9 stratum (>244 ng/ml). The primary analysis of percent change from baseline (in the form of ratio) in UPCR over 26 weeks will be performed in the subjects in ITT population whose UPCR is abnormal at baseline using a mixed effect model for repeated measures (MMRM) analysis with treatment group, visit, treatment-by-visit interaction and baseline as a covariate. The abnormal UPCR value is defined as UPCR ≥ 0.15 g/g. Subjects will be considered as repeated measure units over visits. Point estimates and corresponding 95% confidence intervals will be estimated for the difference between avacopan and placebo across 26 weeks using a simple contrast from the model.

To alleviate the skewness of the data, UPCR will be log_e-transformed before entering into the MMRM analysis. Least squares mean differences between avacopan and the placebo group in the percent change from baseline to Week 26 log(UPCR) will be back transformed to obtain the estimate for the baseline-adjusted reduction from control in UPCR. Corresponding P-values will also be presented.

In the MMRM model, missing data will not be imputed. Toeplitz covariance matrix will be used to model within-subject variance-covariance structure for the model errors. If the model does not converge using the Toeplitz covariance matrix, AR(1) covariance matrix will be used. If convergence is still not met, then compound symmetry (CS) will be used.

The code used to generate the MMRM analysis will be similar to the following:

```
Note:
TRT01AN = randomized treatment group (numeric): 1=Placebo, 2=Avacopan
VISITN = Visit Number
LR2BASE = Ratio of Visit Value to Baseline Value (log-transformed)
LBASE = Baseline value of response (log transformed)
proc mixed data=lablog;
class SUBJID VISITN TRT01AN(ref='1');
model LR2BASE = TRT01AN VISITN TRT01AN*VISITN LBASE/
solution cl ddfm=kr;
Repeated VISITN / TYPE=TOEP sub=SUBJID;
**use AR(1) if no convergence, then CS;
lsmeans VISITN*TRT01AN / alpha=0.05 cl pdiff slice=VISITN;
ods output LSMeans=LSM
```

5.3.1.2 Secondary Analysis

run;

The same analysis as described for the primary analysis will also be performed for the following:

- Percent change from baseline over 26 weeks during the double-blind treatment period in the combined C5b-9 strata (subjects with elevated C5b-9 blood levels and non-elevated C5b-9 blood levels)

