A sensitivity analysis will be performed using a pattern mixture model with multiple imputation for missing data under the missing not at random (MNAR) assumption using the same approach as described for the primary analysis. The steps to carry out the multiple imputation and analysis are described below:

The 6 lesions in disease activity and 2 lesions in disease chronicity with continuous results will be imputed using SAS code below, using the same seed numbers as specified for the primary imputation method.

```
**** Imputation at Week 26, Continuous variable;
Proc MI Data= ERT (Where=(PARAMCD=" ")) Seed= ##### Nimpute= 100
Minimum= . . 0
Maximum= . . 100
OUT= PMMnum_IM26;
Class TRT01PN DISTYPE RENTRANS;
Var DISTYPE RENTRANS BL W26;
Monotone Reg(W26/Details) ;
MNAR Model(W26/ modelobs=(TRT01PN='1')) ;
Run;
```

The 1 classification variable in disease activity and 2 classification variables in disease chronicity will be imputed using SAS code below using the same seed numbers as specified for the primary imputation method.

**** Week 26, Classification variable; Proc MI Data= ERT (Where=(PARAMCD=" ")) Seed= ##### Nimpute= 100 OUT= PMMcat_IM26; Class DISTYPE RENTRANS TRT01PN BL W26; Var DISTYPE RENTRANS TRT01PN BL W26; Monotone Logistic(W26= DISTYPE RENTRANS TRT01AN BL / Details likelihood=AUGMENT); MNAR Model(W26/ modelobs=(TRT01PN='1')) ; Run;

The ANCOVA analysis will be performed as detailed above for the primary imputation method using the imputation datasets.

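### The categorical-lesion step of the MNAR sensitivity analysis keeps treatment in a model fitted to one arm only, so imputation of avacopan patients from the placebo model is not guaranteed

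*SAP*

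**What the plan says.** SAP 5.2.3 makes a firm commitment: "A sensitivity analysis will be performed using a pattern mixture model with multiple imputation for missing data under the missing not at random (MNAR) assumption". It is to follow the primary analysis's approach, and SAP 5.3.3 carries the sensitivity analyses over to the chronicity index. The code is in Appendix 12.3, in two steps.

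- **Both steps** restrict the fitting data with the same statement: "MNAR Model(W26/ modelobs=(TRT01PN='1" (the excerpt stops just before the closing quote mark and brackets).
- **Continuous lesions** (six activity, two chronicity): the class list is "Class TRT01PN DISTYPE RENTRANS" and the variable list is "Var DISTYPE RENTRANS BL W26". Treatment is in the class list but is not a predictor.
- **Categorical lesions** (one activity, two chronicity): the variable list and the model read "Var DISTYPE RENTRANS TRT01PN BL W26; Monotone Logistic(W26= DISTYPE RENTRANS TRT01AN BL / Details likelihood=AUGMENT", and `TRT01PN` is also in the class list. Treatment is in the variable list under one name and in the effects under another.

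The numeric coding is given in SAP 5.3.1.1, for the second name only: "TRT01AN = randomized treatment group (numeric): 1=Placebo, 2=Avacopan". The Appendix 12.3 notes for `TRT01PN` give no numbers, only the order placebo then avacopan.

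The primary Week 26 imputation code in Appendix 12.3 runs separately by `TRT01PN` and has no treatment covariate.

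**The concern.** Fitting on one arm and imputing both arms from that fit makes sense only if treatment is not a predictor. The continuous step respects this and the categorical step does not, so two halves of one analysis use incompatible models. The printed categorical step also names a model effect that it does not list.

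This is the only MNAR analysis that the SAP says will be done. The other sensitivity analysis in 5.2.3 is optional and reuses the primary imputation. Missing Week 26 biopsies were foreseen: SAP 3.1.8 lists sites not allowing biopsy among the COVID-19 effects. The chronicity index, where half the lesions are affected, is tested at 0.05 once the activity index succeeds in the same stratum (SAP 3.1). A pre-specified robustness check on these endpoints should not turn on how a program resolves a singular fit.

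**Working it through.** The plan gives no figure for this step, so there is nothing to reproduce. The check is of the code.

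**1. Which lesions.** SAP 5.2.1 names six activity lesions that are imputed as continuous values. Interstitial inflammation is the one left out, so it is the categorical activity lesion. It scores 0 to 3 in an index of 0 to 21, so its share is at most 3/21 = 14%. Appendix 12.3 counts two of the four chronicity lesions as categorical.

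**2. Names.** `TRT01AN` is in the effects but in neither list of that step. The rest of this check assumes that it is corrected to `TRT01PN`, or that both names hold the randomised group.

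**3. Identification.** For an ordered score, write logit P(W26 ≤ k) = a_k + b′x + g·t, where t is the treatment code. In the fitting data t equals one constant c. For any number d, replacing a_k by a_k + d·c and g by g − d leaves every fitted value unchanged. For a patient in the other arm, with code c′, the same replacement moves the linear predictor by d·(c − c′), which is not zero. The data therefore cannot fix the prediction for that arm. This holds whichever arm is coded 1.

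**4. Rank check.** The design has an intercept, disease type, transplant, treatment, and three indicators for a four-level baseline score: 1 + 1 + 1 + 1 + 3 = 7 columns. It used about 22 patients per arm (SAP 2.2.2).

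| Fitting data | Columns | Rank |
|---|---|---|
| Both arms, treatment in | 7 | 7 |
| Placebo only, treatment in | 7 | 6 |
| Placebo only, treatment out | 6 | 6 |

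The rows with treatment in were the same under effect coding and under both reference codings.

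**5. What avacopan patients would receive.** This is an illustration with assumed inputs: 2,000 simulated placebo-only fits of 22 patients, a lesion simplified to present or absent, one baseline covariate, and a true mean placebo probability of 0.68.

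| Handling of the unidentified term | Mean probability for avacopan patients |
|---|---|
| Removed, set to zero, or reference coding with placebo = 0 | 0.675 |
| Effect coding, constant split evenly between intercept and treatment | 0.50 (the two cancel) |
| Assumed form of likelihood augmentation, point estimate | 0.674 |
| Same, random draws as used for imputation | 0.58, SD 0.37 |

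In the last case the SD of intercept minus treatment is about 3.9 on the logit scale, so the draws are mostly noise.

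**6. Size on the endpoint.** Assume a baseline activity score of 6 to 12 and an error of one point in the imputed lesion. For that patient the percent change moves by 1/12 = 8 to 1/6 = 17 percentage points. Averaged over 22 patients, one such patient moves the arm mean by 8.3/22 = 0.4 to 16.7/22 = 0.8 points. Four such patients, all wrong in the same direction, move it by 1.5 to 3.0 points. The design difference is 35 points (SAP 9).

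**The case against.** A reader might infer that avacopan patients are not imputed as placebo. The documents do not support that. If the unidentified term is set to zero, or placebo is the zero reference level, the step gives the intended result. The software's behaviour is not described in the documents, and SAS was not run. Only the absence of a guarantee is shown.

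A reader might also infer that the MNAR analysis is worthless. That goes too far. Six of seven activity lesions go through a step with no such fault, and the completer and per-protocol analyses exist too, although they do not test MNAR.

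Two further objections have weight. The printed code is a template with blank placeholders, so the one-letter difference in names may be a typing slip. If it causes an error, the programmer will see it and nothing is wrongly imputed. Also, the SAP text says only pattern mixture and MNAR; imputation from the placebo model is inferred from the fitting restriction.

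These points narrow the claim without removing it. Treatment is in the categorical model under either name, and correcting the name leads directly to the singular fit. That the SAP does not state its reference assumption is a further reason to write it down.

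**Conclusion.** The point stands as a code defect of limited reach. The categorical MNAR step may not run as printed. With the name corrected, its treatment coefficient is unidentified, and imputation of avacopan patients from the placebo model depends on software handling. It touches one activity lesion and two chronicity lesions, only where they are missing at Week 26, and only in this sensitivity analysis. The primary imputation, done by arm, is unaffected.

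The likely effect on the activity result is small unless several avacopan patients lack a Week 26 value; the documents do not say how many do. The chronicity index is more exposed, because half of its lesions are affected. The conclusion assumes that both treatment variables hold the randomised group. Reading the reference arm as placebo also assumes that they share the coding in SAP 5.3.1.1, but the identification failure does not depend on that coding.

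**What to change.** In the categorical MNAR step of Appendix 12.3:

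- delete `TRT01PN` from the variable list and `TRT01AN` from the logistic effects;
- keep `TRT01PN` in the class list, where the fitting restriction uses it, as in the continuous step;
- use one treatment variable throughout the imputation code and give its numeric coding there.

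In 5.2.3 and 12.3, add a sentence saying that missing values in both arms are imputed from the model fitted to placebo patients. SAP 5.2.1 and 12.3 list treatment group in the primary imputation model. Without that sentence, the reference to the primary approach can be read as requiring treatment in the MNAR model as well.

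With treatment removed, the placebo-only design has full rank (6 of 6), and the simulated avacopan patients receive 0.675 against a true 0.68. The cost is a small code edit and a sentence in each section. No new data are needed, and the primary analysis and sample size do not change. The production program should be checked for the same lines before database lock.

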12.4 Preferred Terms of Adverse Events Potentially Associated with Liver Injury

Alanine aminotransferase increased Aspartate aminotransferase increased Alcohol withdrawal syndrome

12.5 Preferred Terms of Adverse Events Indicating WBC Count Decrease

Leukopenia Lymphopenia Neutropenic sepsis Lymphocyte count decreased Neutrophil count decreased

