4.4. Removal of Patients from Therapy

Investigators must clearly distinguish between discontinuation of study drug treatment (avacopan or placebo) and withdrawal from the study. Patients who discontinue study drug treatment or who initiate medication changes (including those prohibited by the protocol that comprise treatment failure) will not be automatically withdrawn from the study, but all efforts must be made to continue to follow the patients for all regularly scheduled visits.

Investigators must take appropriate measures to make sure that patients are motivated to comply with all requirements of the protocol in order to minimize the amount of missing data. Patients who discontinue study treatment early or initiate medication changes (including those prohibited by the protocol) should continue to be followed for all regularly scheduled visits for safety and efficacy assessments. Investigators and their staff must take measures to actively maintain contact with their patients in the study, such as telephone calls, texts, or emails between visits, and offers for transportation support to visit the study site.

Patients may be withdrawn from the study for only one of the following two reasons:

1. Patient withdrawal of consent to contribute additional outcome information;
2. Loss to follow-up.

Patients may discontinue study drug treatment for any of the following reasons:

1. Patient withdrawal of consent;
2. The Investigator may discontinue study drug treatment if, in his/her clinical judgment, it is in the best interest of the patient;
3. The Sponsor may request discontinuation of study drug treatment for safety reasons. If a patient develops any of the following lab abnormalities:

If a patient develops ALT or AST $>3x$ ULN, additional testing should be performed immediately and repeated in one week to assay for total and fractionated serum bilirubin concentration, serum albumin concentration, and prothrombin time or INR, in addition to repeat transaminase (ALT, AST) testing. In addition, if a patient develops Grade 3 or greater increased hepatic transaminases (>5 times the upper limit of normal), or if a patient develops Grade 2 or greater increased transaminases (>3 times the upper limit of normal) with elevation of bilirubin to >2 times the upper limit of normal, dosing with study drug must be paused in this patient.

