Study medication must be permanently discontinued ([FDA Guidance 2009](#)) if any of the following markers of hepatic injury and/or impaired liver synthetic function are observed, and cannot be attributed to a reversible etiology unrelated to study medication (e.g., cholelithiasis):

- ALT or AST $>8x$ ULN
- ALT or AST $>5x$ ULN for more than 2 weeks
- ALT or AST $>3x$ ULN and (Total Bilirubin $>2x$ ULN or INR >1.5)
- ALT or AST $>3x$ ULN with the appearance of fatigue, nausea, vomiting, right upper quadrant pain or tenderness, fever, rash, and/or eosinophilia ($>5\%$)

If a patient develops Grade 3 or greater leukopenia (WBC count $<2 \times 10^9/L$) or neutropenia ($<1 \times 10^9/L$), or Grade 4 lymphopenia ($<0.2 \times 10^9/L$), then study drug (avacopan or placebo) must be paused in this patient. In addition, if a patient develops Grade 2 leukopenia (WBC count $<3 \times 10^9/L$, but $\geq 2 \times 10^9/L$), the patient must be followed closely for infection and for further significant reduction (reduction by an additional $0.5 \times 10^9/L$ or more, or to $<2 \times 10^9/L$) in WBC count; if either occurs, then study drug must be paused in this patient. Study drug may be resumed only if the abnormal value returns to normal and the Investigator deems resumption to be appropriate.

If a patient develops Grade 3 or worse CPK increase (>5 times the upper limit of normal), dosing with study drug must be paused in this patient. Study drug may be resumed only if the CPK returns to normal levels.

Patients who experience deteriorating renal function based on an increase in serum creatinine of at least 50% (confirmed by a repeat measurement after at least 2 weeks) which is otherwise not explained (e.g., dehydration, new medication), or an increase in proteinuria of >3 g/g creatinine (confirmed by a repeat measurement after at least 2 weeks) from Screening or baseline during the 52-week treatment period, will exit the treatment phase of the study and be treated at the discretion of their physician. The increase of serum creatinine or proteinuria will be calculated from the higher value that is measured either at Screening or baseline. They will remain in the study for follow up and complete the remaining study visits and procedures. If a patient refuses further study participation, the Early Termination visit procedures will be performed, if possible. These patients will be considered treatment failures.

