7.2.4.6. Laboratory Abnormalities

Safety laboratory tests are performed frequently over the course of the study. Laboratory reports with abnormal findings will be reviewed by the Investigator. The Medical Monitor will review notably abnormal laboratory results according to the Safety Monitoring Plan.

Please see [Section 4.4](#) for guidance on laboratory abnormalities (white blood cell count, neutrophil count, lymphocyte count, AST or ALT and other lab abnormalities of impaired liver function or hepatic toxicity, CPK increase, creatinine or proteinuria increases) that would prompt pausing or permanently discontinuing study drug (avacopan or placebo).

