2.3.7 Safety Endpoints

2.3.7.1 Adverse Events

Safety endpoints include subject incidence of treatment-emergent serious adverse events, treatment emergent non-serious adverse events, and withdrawals from the study drug or clinical trial due to adverse events.

An adverse event will be considered treatment-emergent (TEAE) if the start date of the event is on or after the date of administration of the first dose of study medication. All reported adverse events will be classified by system organ class and preferred term using the Medical Dictionary for Regulatory Activities (MedDRA) (version 19.1). Treatment-emergence will also be determined based on the Safety Populations defined in Section 3.2.3.

The relationship to avacopan/placebo will be determined by the Investigator. The sponsor will perform a safety analysis based on an aggregate analysis across the safety database as well as the assessment of individual cases of interest.

A serious adverse event (SAE) is defined as any untoward medical occurrence that at any dose results in death, is life-threatening, requires or prolongs hospitalization, results in persistent or significant disability or incapacity, is a congenital anomaly or birth defect, or is an important and significant medical event that, based on appropriate medical judgment, may jeopardize the subject and/or may require medical or surgical intervention to prevent one of the other outcomes defining serious.

In addition, specific TEAEs of interest will be presented by treatment group (see Section 6.3).

2.3.7.2 Clinical Laboratory Assessments

Safety endpoints related to clinical laboratory assessments include change from baseline and shifts from baseline in all safety laboratory parameters, including blood chemistry, hematology, and urinalysis.

Clinical laboratory assessments will be performed at the visits identified in the Time and Events Table in the protocol:

- Hematology: hemoglobin, hematocrit, red blood cell (RBC) count, white blood cell (WBC) count with differential, platelet count, mean cell hemoglobin, mean cell hemoglobin concentration, mean corpuscular volume

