6.3 Adverse Events

Adverse event results will be provided including number of events and percentages of subjects (subject incidence) affected for the 3 Safety Populations (see 3.2.3 for definitions) separately including the following:

- All treatment emergent serious adverse events by SOC and preferred term
- All treatment emergent serious adverse events by decreasing order of frequency by preferred term
- All treatment emergent non-serious adverse events by SOC and preferred term
- All treatment emergent non-serious adverse events by preferred term by decreasing order of frequency
- All treatment emergent serious and non-serious adverse events by SOC

• All treatment emergent serious and non-serious adverse events by decreasing order of frequency by preferred term

Adverse events will be coded using the Medical Dictionary for Regulatory Activities (MedDRA) Version 20.1.

TEAEs for the Safety Population in each period are defined as an event with a start date on or after the first study drug treatment in each period and up to the final observation in each period. Treatment periods for analysis of adverse event are defined in Section 3.2.3. TEAEs for the All Avacopan Treated Population are defined as an event with a start date on or after the first dose of avacopan up to the final visit.

Adverse events will be listed by treatment group, including all available information of interest such as onset and resolution dates, study day of onset and resolution relative to first dosing day, duration, severity, seriousness, causal relationship to study medication per the investigator, action taken with study medication, and outcome. Separate listings will be provided for TESAEs, TESAEs and TEAEs leading to discontinuation of study drug, and TEAEs of interest.

TEAEs of interest include hepatic enzyme elevations, hypersensitivity Standardized MedDRA Queries (SMQ), infections, decrease in white blood cell count and elevations in creatine phosphokinase (CPK).

The severity of AEs was assessed by the investigator using the following protocol definitions:

- Mild (Grade 1): no limitation of usual activities
- Moderate (Grade 2): some limitation of usual activities
- Severe (Grade 3): inability to carry out usual activities
- Life-threatening (Grade 4): an immediate risk of death
- Death (Grade 5)

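### The preferred-term lists for liver injury and white-cell decrease omit terms that the protocol itself points to, so the special-interest grouping would be incomplete if they are applied as written

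*SAP*

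**What the plan says.** SAP section 6.3 sets out the special-interest categories: "TEAEs of interest include hepatic enzyme elevations, hypersensitivity Standardized MedDRA Queries (SMQ), infections, decrease in white blood cell count", followed by CPK elevations. It promises separate listings for them, and SAP section 2.3.7.1 adds that they will be shown by treatment group.

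Two appendices supply preferred terms. Appendix 12.4, on events potentially associated with liver injury, contains "Alanine aminotransferase increased Aspartate aminotransferase increased Alcohol withdrawal syndrome". Appendix 12.5, on white-cell decrease, contains "Leukopenia Lymphopenia Neutropenic sepsis Lymphocyte count decreased Neutrophil count decreased". Neither says that its terms are examples, neither refers to a standard query, and section 6.3 cites neither. Hypersensitivity, by contrast, is defined by a standard MedDRA query.

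The protocol treats these areas as important. Section 4.4 has study-drug pausing rules for leukopenia, neutropenia and lymphopenia. On the liver side it refers to transaminase rises "with elevation of bilirubin to >2 times the upper limit of normal", and it has a further rule that applies where "markers of hepatic injury and/or impaired liver synthetic function are observed". Section 7.2.4.6 summarises the scope as "white blood cell count, neutrophil count, lymphocyte count, AST or ALT and other lab abnormalities of impaired liver function or hepatic toxicity", plus CPK, creatinine and proteinuria.

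**The concern.** A special-interest category exists to pool related terms. In a small trial, a signal spread over several preferred terms, each with one or two patients, is easy to miss unless the terms are counted together. A list that leaves out the plainest names for the event defeats that purpose.

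The gap falls where the sponsor has been most watchful. Protocol section 12.3.2 says that hematology monitoring was made more frequent and the pausing rules were modified after DMC review, partly because of an observation in this trial. Protocol section 7.2.4.1 also asks sites to report the clinical event rather than the laboratory abnormality where possible. That may steer some liver events towards clinical terms, and the liver list has none.

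**Working it through.** The plan gives no figure that depends on the lists, so there is nothing to reproduce. The check is a comparison of terms, followed by arithmetic for scale.

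**White-cell list (SAP 12.5, five terms) against the protocol**

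| Cell line | Condition term listed? | Count-decrease term listed? | Where the protocol raises it |
|---|---|---|---|
| Lymphocytes | Yes (*Lymphopenia*) | Yes | 4.4 pausing rule |
| Neutrophils | No (*Neutropenia* absent; only *Neutropenic sepsis*) | Yes | 4.4 pausing rule |
| Total white cells | Yes (*Leukopenia*) | No (*White blood cell count decreased* absent) | 4.4 pausing rule; 12.3.2, Phase 1 adverse event, 3.4% avacopan, 0% placebo |

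The list is uneven on its own terms. Lymphocytes have both forms and the other two lines have one each. Neutropenia complicated by sepsis would count, but uncomplicated neutropenia coded to *Neutropenia* would not.

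**Liver list (SAP 12.4, three terms) against the protocol**

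| Concept | In the list? | Where the documents raise it |
|---|---|---|
| ALT or AST increase | Yes | Protocol 4.4; SAP 6.3 |
| General hepatic-enzyme or transaminase increase | No | SAP 6.3 category name; protocol 4.4 |
| Bilirubin increase | No | Protocol 4.4 |
| Clinical liver injury | No | Protocol 4.4; the title of 12.4 itself |
| *Alcohol withdrawal syndrome* | Yes | Nowhere else in either document |

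**Share of an arm represented by one ungrouped event**

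- Planned size is 22 per arm in each of two C5b-9 strata (protocol 8.8). The Safety Population has no stratum restriction (SAP 3.2.3), so a planned arm is 22 + 22 = 44.
- One event: 1/44 = 2.3%.
- If an arm held only 22 patients: 1/22 = 4.5%.
- SAP section 10 says the non-elevated stratum is small. If the elevated stratum fills as planned, the figure lies between these two.

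**Chance that such an event arises (illustration only)**

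Assume the Phase 1 rate for decreased WBC count, 3.4%, applied here. The chance of at least one affected patient among n is 1 − (1 − p)^n.

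| p | n = 22 | n = 44 |
|---|---|---|
| 1% (assumed) | 20% | 36% |
| 3.4% (Phase 1) | 53% | 78% |
| 5% (assumed) | 68% | 90% |

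At 3.4% the expected number of patients is 22 × 0.034 = 0.75 or 44 × 0.034 = 1.5. Phase 1 enrolled healthy volunteers, so the rate is a rough guide to whether the omission could matter, not a forecast.

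**The case against.** The strongest reply is that nothing is lost from the safety report. SAP section 6.3 tabulates all serious and non-serious treatment-emergent events by preferred term in each of the three safety populations, so an event coded to *Neutropenia* appears there under its own name. SAP section 6.4 adds CTCAE-graded incidence and shifts for ALT, AST, total bilirubin, alkaline phosphatase, neutrophils, lymphocytes and leukocytes. The protocol's pausing rules are mainly laboratory thresholds, and those tables address them directly. This stands. A reader might infer that the events would vanish from the report, and the documents do not support that. The laboratory cover is only partial: section 6.4 summarises central-laboratory values and merely lists local ones, section 3.1.8 allows for local laboratories used because of COVID-19, and INR is not among the graded parameters.

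A second reply is that the lists may simply record terms already seen in blinded data. Entries as particular as *Alcohol withdrawal syndrome* and *Neutropenic sepsis* suggest this. It is plausible, but the SAP does not say so. Equally, a reader might infer that the lists are closed and that the final analysis is bound to them; the SAP states neither. It says in section 8.1 that the final analysis covers patients still ongoing and those enrolled later, and it gives no rule for updating the terms. Under either reading the text needs to be settled.

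Third, section 6.3 speaks of enzyme elevations, and bilirubin is not an enzyme. That is fair, but the title of Appendix 12.4 is wider. Finally, one might argue that the lists should hold terms such as agranulocytosis or drug-induced liver injury because the protocol singles them out. It does not: the first appears nowhere in the text and the second only in the title of a cited guidance. The point does not rely on either.

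**Conclusion.** The point holds as a defect in how two special-interest groups are defined. As written, Appendices 12.4 and 12.5 omit *Neutropenia*, *White blood cell count decreased*, and any bilirubin, general hepatic-enzyme or transaminase, or clinical liver-injury term. They include one term that is not itself a liver finding. Applied literally, they would leave such events out of the special-interest listings and the by-group presentation.

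The consequence is limited to grouping. No efficacy result and no main adverse-event table changes. A reader might take 4.5% of an arm as the size of one missed event, but that uses one stratum's denominator. Across both strata at planned enrolment it is 2.3%, with 4.5% as the upper end if an arm held only 22.

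This rests on three assumptions: that the two appendices are complete in the available copy of the SAP, that they are meant to define the categories in section 6.3 (no other definition is given), and that events of these kinds can be coded to terms other than those listed. Nothing in the documents shows that any event has been coded to an omitted term.

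**What to change.** Before unblinding for the primary analysis:

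- Cite Appendices 12.4 and 12.5 in SAP section 6.3, and state that they define the two categories for all data, including the final analysis.
- Define each category by a standard MedDRA query, as is already done for hypersensitivity. Otherwise extend the lists to cover at least *Neutropenia*, *White blood cell count decreased*, and bilirubin, hepatic-enzyme or transaminase, and clinical liver-injury terms.
- Justify *Alcohol withdrawal syndrome* or remove it.
- Reconcile the MedDRA version, which is 19.1 in SAP section 2.3.7.1 and 20.1 in section 6.3, and check the terms against the version chosen.

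The cost is a small SAP edit and possibly slightly more events in the special-interest outputs. No new data are needed.
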